All video is time- and date-stamped and transferred to our servers daily through wireless communication. The DriveCam technology will also be programmed to record the onset and offset of driving. In addition, global positioning capability within DriveCam will allow tracking of miles driven for each drive. Using this information, we will be able to determine how many hours and miles the car was driven by the teen. We will also be able to determine from this video whether other people (e.g., parents, other adults, or friends) were present in the car during each driving episode. We will also use an established coding system⁸ to record general background (e.g., time of day) and environmental (e.g., weather, road type) variables surrounding the MVC.

Any g-force event that exceeds .6 g-force will be coded using three primary codings: 1) incidents (i.e., a threshold exceedance in which the driver’s action, either intentional or unintentional, was responsible for a safety-relevant event), 2) crashes (i.e., collision with another vehicle or object), and 3) near-crashes (i.e., an evasive maneuver performed to avoid a MVC). Video recordings of the driver will be coded for whether an

extended glance away from the roadway preceded the event, along with the length of the glance away from the roadway and the temporal proximity of that glance to the actual event. Also, since most incidents will be preceded by an extended glance away from the roadway, incident-related video recordings will not provide an adequate sample for examining typical eye glance behavior. Hence, we will also collect and code an additional 60 randomly-selected 20-second clips from low threshold events.

The primary outcomes we will obtain from these data will include the number of incidents, crashes, and near-crashes per hour driven. Also, we will be able to determine the number of incidents preceded by ≥ 2 sec glance away from roadway per hour driven as well as a general number of extended glances away from the roadway from the random clips.

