The hypotheses listed above will use the same statistical modeling. For each analysis, every randomized teen will be kept in the analyses (i.e., intent-to-treat approach). Mixed factorial ANCOVAs will be used to analyze the data. The two independent variables in the analyses will be Intervention (FOCAL+ vs. Sham Intervention) and Time (immediately after initial training, and 1-, 4-, 8- and 12-months post- randomization). Months of driving experience will be covaried. To test Hypotheses 1, the primary dependent variable will be the number of extended (>2 sec) glances away from the roadway during driving simulation. Secondary analyses testing Hypotheses 1 will focus on other visual attention outcomes across the intervention groups including number of extended glances away from the roadway during the road test.

To test Hypotheses 2, the primary dependent variable will be SDLP during driving simulation. Secondary outcomes for Hypotheses 2 include 1) number of MVCs and reaction time to unexpected events during driving simulation, 2) number of lane crossings and proportion of time out of lane during the road test, 3) number of incidents, near-crashes, and crashes per hour during DriveCam monitoring; and 4) rates of MVCs from teen's driving records. When examining DriveCam outcomes, we will add a time-varying covariate indicating medication use to account for the effects of medications on driving outcomes.

For each statistical model, the term of interest is the main effect of Intervention. A significant main effect of Intervention would indicate that the FOCAL+ intervention significantly impacted eye glance and driving outcomes. A significant Intervention effect will be followed up with post-hoc comparisons to determine the direction and locus of the effect, including whether intervention effects were maintained at 4-, 8-and 12-months post-training. Though we expect intervention effects to be strongest immediately following training (1-month), we predict that FOCAL+ will be more effective than the sham intervention for ADHD teens at each time point.

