5.1 Study Objectives

The goal of the proposed research is to empirically test the effectiveness of the FOCAL+ intervention in comparison to a sham intervention at improving visual attention and driving performance in teens with ADHD. Specifically, we will conduct a randomized controlled trial using 152 teens diagnosed with ADHD. Teens will be randomized to receive 5 training sessions of the FOCAL+ intervention or a sham intervention. 1-month and 6-months post-training, teens' driving skills, including frequency of extended eye glances, will be assessed during driving simulation. In addition, at the conclusion of training, a DriveCam camera system in their car will record naturalistic driving. The DriveCam will remain in their car until 12-months post-training. Finally, we will acquire the teen's driving records for the period they are in the study.

Primary Objective: We will examine the effectiveness of the FOCAL+ intervention versus sham intervention at decreasing rates of extended glances away from the roadway and improving driving performance among teens with ADHD at 1-month post-training, and 6-months post-training.

Secondary Objective: We will examine the effectiveness of the FOCAL+ intervention versus sham intervention in decreasing rates of extended glances away from the roadway, frequency of driving events, crashes, and crashes/near crashes as measured by in-car technology (DriveCam) during the 12-months post-training.

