The DriveCam device has two integrated cameras. One facing the forward roadway; the other facing the driver. If the built-in accelerometer detects a ≥ 0.6 forward or lateral g-force event, the device records the 8 secs before and 4 secs after the triggered event. Four events will be randomly selected for coding if a teen had >4 events in a week. Trained coders will code the onset and offset of visual glances away from the roadway such that a count of extended eye glances (≥ 2 seconds) will be obtained. Additionally, coders will record whether the event captured a crash (i.e., contact between the vehicle and another object) or near crash (i.e., an evasive maneuver performed to avoid a MVC). The two secondary endpoints that will be used from the DriveCam video events will be as follows:

1) Events that Included an Extended Eye Glance: During the 5-seconds preceding the event until the 1-second after the g-force event, if a glance away from the roadway was ≥ 2 seconds, the event will be identified as having a long glance. Events that do not include a glance away from the roadway ≥ 2 seconds during the 5-seconds preceding the event until the 1-second after the g-force event will be identified as not having a long glance.

2) Events that Included Crashes and Near Crashes: Coders will make a determination after viewing each event whether the event included or did not include a crash or near-crash. Crashes and near crashes (CNC) will be combined due to low crash rates and near-crashes are an established surrogate for crashes (Guo, Klauer, Hankey, & Dingus, 2010).

6 Study Methods

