10.6 Secondary Efficacy Analyses

All analyses of secondary endpoint DriveCam data will be analyzed using GEE. GEE analyses assuming a Poisson distribution and natural logarithmic link function will be used to analyze individual DriveCam events per participant (random effect) and assess the relative risk of each dichotomous outcome (i.e., presence/absence of long-glance, crash/near crash per event). For these secondary analyses, relative risk ratios with 95% confidence intervals will be computed rather than testing statistical significance (Zou, 2004). Note that the widths of confidence intervals will not be adjusted for multiple comparisons and no definite conclusions can be drawn from these results.

11 Safety Analyses

The PI ([name]) will be responsible for detecting, documenting, and reporting events that meet the definition of an Adverse Event (AE) or Serious Adverse Event (SAE). Safety data will be tracked and reported as required by Clinicaltrials.gov. Three tables summarizing adverse events will be created:

- All-Cause Mortality: A table of all deaths due to any cause, with number and frequency of such events in each arm/group of the clinical study.
- Serious Adverse Events: A table of all serious adverse events with number and frequency of such events in each arm/group of the clinical study. See Serious Adverse Events definition

below.

- Other (Not Including Serious) Adverse Events: A table of events within any arm of the clinical study with number and frequency of such events in each arm/group of the clinical study. See Adverse Events definition below.

These events will be analyzed and reported for All Randomized Study Participants and by treatment group at the end of the study period. The only SAE that will be analyzed in the interim is events with a shock value (i.e., indicating a collision) as recorded by DriveCam technology (See 8.5 Interim Analyses for more information).

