 - c. Due to the cost, the MEMSCap Medication Event Monitoring System was dropped from the study protocol. We replaced daily monitoring of ADHD medication use using self-reported measure of medication administered at baseline and each follow-up visit.

10/30/2019

- 1) **Increase in sample size based on attrition for 6-month driving simulator visit.** Our initial protocol proposed to randomize 136 participants; however, this randomization goal was based on successfully collected data from 136 at the 1- and 6-month driving simulations—the source of our primary endpoints. When we reached 136 recruited participants, we have estimated a new attrition rate based on data collected thus far. This calculation suggests that we need to over-recruit to a randomized sample size of 152 to achieve 136 participants with 1- and 6-month simulator outcomes (primary endpoints).

1/11/21

- 1) **BMV records no longer an outcome of interest.** Once all BMV records were collected, we examined the frequency of BMV-reported MVCs. We also compared these rates to the frequency of behaviorally coded MVCs captured by DriveCam technology. The frequency of MVCs according to BMV records was 19 total MVCs across the entire sample over the course of 1-year of driving. According to DriveCam codings of collisions, there were >100 crashes across the entire sample over the course of 1-year of driving. Thus, the research team decided that BMV crashes were not an accurate outcome measure and therefore it would no longer be used as an outcome measure.

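### The SAP names DriveCam crashes as an objective in their own right but estimates an effect only for crashes and near-crashes combined

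*Combined protocol and SAP*

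**What the plan says.** Protocol section 5.e.1 codes DriveCam events above the g-force threshold as incidents, crashes or near-crashes and gives each an hourly rate: "The primary outcomes we will obtain from these data will include the number of incidents, crashes, and near-crashes per hour driven". The word primary there means the main DriveCam measures; DriveCam as a whole is a secondary outcome source. Protocol section 5.f.2.a repeats the list among the secondary outcomes for Hypothesis 2: "number of incidents, near-crashes, and crashes per hour during DriveCam monitoring".

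SAP section 5.1 keeps the separation. Its secondary objective covers "frequency of driving events, crashes, and crashes/near crashes as measured by in-car technology (DriveCam".

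SAP section 5.2 then merges the two: "Crashes and near crashes (CNC) will be combined due to low crash rates and near-crashes are an established surrogate for crashes". Scoring is one indicator per event: "Coders will make a determination after viewing each event whether the event included or did not include a crash or near-crash". Section 6.4 carries the merged variable forward. Section 10.6 fits a Poisson, log-link GEE to "assess the relative risk of each dichotomous outcome (i.e., presence/absence of long-glance, crash/near crash per event", reporting relative risks with 95% confidence intervals and no significance test.

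On the number of crashes, the 1/11/21 entry in SAP section 14.6 explains why driving records were dropped: "The frequency of MVCs according to BMV records was 19 total MVCs across the entire sample", whereas on DriveCam "there were >100 crashes across the entire sample over the course of 1-year of driving".

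**The concern.** The current SAP states an objective for crashes and provides no endpoint or model that answers it. None of the four endpoints in section 5.2 is crash-only. The driving-record crash outcome was dropped (section 14.6), and the protocol's simulator crash count is not among the SAP endpoints. Protocol Aim 2 still mentions motor vehicle crashes, and SAP section 14.5 records no change of aims.

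The components are not interchangeable for this intervention. A near-crash is defined as an evasive manoeuvre made to avoid a crash, and training that brings the eyes back to the road sooner could affect the two differently. A composite that scores them alike mixes the two effects in proportion to how common each is. The rationale in both documents concerns crashes, injuries and deaths, so readers will want to know whether a CNC result reflects crashes.

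**Working it through.** **Is there a figure to reproduce?** No. Neither document gives an event target or a DriveCam-specific power calculation. The protocol's general claim of more than 90% power for driving performance carries over the effect size assumed for glances.

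**Step 1: trace the objective to an analysis.**
- Objective (SAP 5.1): crashes, and separately crashes/near crashes.
- Endpoint (SAP 5.2, 6.4): the combined indicator only.
- Model (SAP 8.4 secondary analyses, 10.6): long glance and combined crash/near crash only.
- Crash-only data by arm (SAP 8.5.1, 8.5.8): monthly and cumulative counts for safety review, with no effect estimate or interval.

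The crash objective stops at section 5.1.

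**Step 2: what the composite can hide.** Let s be the share of crashes among control-arm CNC events, and assume each event falls in one category. For per-event relative risks,

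RR(CNC) = s × RR(crash) + (1 − s) × RR(near-crash).

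The documents do not give s, so a range is assumed.

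| s | RR(crash) 0.6, RR(near-crash) 1.0 | RR(crash) 1.0, RR(near-crash) 0.6 |
|---|---|---|
| 10% | 0.06 + 0.90 = 0.96 | 0.10 + 0.54 = 0.64 |
| 30% | 0.18 + 0.70 = 0.88 | 0.30 + 0.42 = 0.72 |
| 50% | 0.30 + 0.50 = 0.80 | 0.50 + 0.30 = 0.80 |

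A 40% reduction in crashes can appear as 4%, and a sizeable CNC benefit can arise with no effect on crashes. At s = 50% the two opposite situations give the same CNC result.

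**Step 3: is a crash-only estimate feasible?** Inputs are 152 randomized teens, 1:1 allocation and more than 100 DriveCam crashes; 100 is used as a floor. That is at least 100/152 = 0.66 crashes per teen, against 19/152 = 0.125 in driving records. With E crashes split about evenly and overdispersion φ (assumed; none is given),

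SE(log ratio) ≈ √(4φ/E), and the 95% limits divide and multiply the estimate by exp(1.96 × SE).

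| φ | SE at E = 100 | 95% factor | Ratio detectable with 80% power |
|---|---|---|---|
| 1 | 0.200 | 1.48 | 0.57 |
| 1.5 | 0.245 | 1.62 | 0.50 |
| 2 | 0.283 | 1.74 | 0.45 |
| 3 | 0.346 | 1.97 | 0.38 |

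With 19 crashes and φ = 1 the factor would be 2.46. The DriveCam count therefore supports an estimate with an interval, but is well powered only for large effects.

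**The case against.** The case for leaving the plan alone has real weight.

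- **Low crash rates against more than 100 crashes.** A reader might infer that the SAP contradicts itself. It does not. The endpoint is per event and the total number of events is not given: 100 crashes would be 10% of 1,000 events or 1% of 10,000 (both totals assumed). The count weakens the phrase as a reason not to report crashes, but does not disprove it.
- **Surrogacy.** The SAP's second reason for combining does not depend on the crash count. It supports keeping CNC as the endpoint, but does not remove the need to show the components.
- **The log.** A reader might infer that the merge is unrecorded. Section 14.7 does mention a binary crash/near-crash indicator while describing the model. It is missing from the outcomes changes in section 14.6, and section 14.7 gives no reason for combining.
- **Safety monitoring.** A reader might infer that a rise in crashes would go unseen. Sections 8.5.1 and 8.5.8 compare crash counts by arm every month, section 11.5 lists crash involvement as an anticipated adverse event, and section 11 tabulates adverse events by arm. What is absent is a relative risk with an interval.
- **Complete masking.** A reader might infer that CNC would show nothing if training turned crashes into near-crashes. With 50 crashes per arm assumed and 30% converted, (35 + 15 + N)/(50 + N) = 1.00 for any number N of control-arm near-crashes, with equal event totals in the two arms. That requires no near-crash to be prevented. If 30% of near-crashes are also prevented, the ratio is (50 + 0.7N)/(50 + N) = 0.80 at N = 100 and 0.74 at N = 300, much nearer the crash ratio of 0.70.
- **Status.** This is a secondary endpoint without a significance test, and section 10.6 already disclaims definite conclusions. That limits the severity; it also means low power is no bar to reporting an interval.

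**Conclusion.** The point holds as a gap between objective and analysis. SAP section 5.1 and the protocol treat crashes as an outcome in their own right, and no crash-only effect is estimated. A CNC relative risk therefore cannot be attributed to crashes or to near-crashes. How far it could differ from the crash effect depends on the unknown share s: a crash RR of 0.6 appears as 0.96 to 0.80 over assumed shares of 10% to 50% when near-crashes are unaffected. These are illustrations, not predictions.

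The documents do not support saying that the reason for merging is false, that the composite is invalid, or that harm would be hidden. This is an inexpensive improvement to a secondary analysis and leaves the primary analysis untouched.

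**What to change.** - **SAP 5.2 and 10.6:** keep CNC as the endpoint. Add crash-only and near-crash-only relative risks with 95% confidence intervals from the same modified-Poisson GEE and covariates (months of driving experience, time the DriveCam was installed), with counts of each by arm. Label them descriptive components and present every CNC result alongside them.
- **SAP 14.6:** record the change from the protocol's separate crash and near-crash outcomes to the combined endpoint, with the reasons.

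The low-crash-rate wording need not be deleted. Nor should there be a rule that a CNC result may be called a crash effect only if the crash-only estimate points the same way. With 50 control crashes and a design effect of 1.5 (both assumed), a true crash RR of 0.8 has SE √(1.5 × (1/40 + 1/50)) = 0.26 and an estimate above 1 about 20% of the time; for a true RR of 0.9 (SE 0.25) it is about 34%.

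The cost is two more model fits and some SAP text. No new coding should be needed, since the crash count in section 14.6 shows that crashes can be identified separately. The downside is a wide crash-only interval: at 100 crashes and an estimate of 0.6, roughly 0.41 to 0.89 with φ = 1 and 0.30 to 1.18 with φ = 3.

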To address ADHD-related driving deficits, we must better understand the mechanism contributing to higher accident risk among individuals with ADHD^{29, 51}. When asked, individuals with ADHD who have been in a MVC cite inattention as the most frequent reason for MVC involvement⁵². In fact, inattention was cited twice as frequently as any other reason (e.g., alcohol use, road conditions, speeding) for causing their MVC⁵². Accordingly, recordings of in-vehicle episodes of visual inattention were the most frequent event immediately preceding collisions among drivers with ADHD⁹, and our own data indicate that teens with ADHD exhibit more extended glances away from the roadway than teens without ADHD²⁸ (see Preliminary Data 5.a.2). Moreover, the number of extended glances away from the roadway mediated ADHD-related deficits in maintenance of a steady lateral lane position while driving, especially during engagement in a secondary task²⁸ (i.e., texting; See Preliminary Data 5.a.3). Extended glances away from the roadway accounts for 32.5% of the variance in standard deviation in lateral position (SDLP) – an indicator of weaving and highly correlated with risk of a real-world traffic accident^{20, 53}. Moreover, accounting for extended glances in the relationship between ADHD status and driving performance makes the path between ADHD status and driving performance non-significant. Though other factors (e.g., impulsivity, drunk driving, fatigue) contribute to ADHD-related driving deficits, our findings and the existing literature³ suggest that diversion of visual attention from the roadway for extended durations when performing secondary tasks significantly contributes to ADHD-related driving deficits and is an appropriate intervention target.

3.d Need for driving interventions targeting teens with ADHD

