We tested whether visual inattention mediated the relationship between ADHD and poor driving. We found that the number of extended glances (≥ 2 secs) away from the roadway mediated ADHD-related deficits in maintenance of a SDLP while driving during distraction (indirect effect $\beta = .10$, $SE = .07$, $p < .05$). Notably, when accounting for extended eye glances as a mediator, the effect of ADHD on SDLP was non-significant ($\beta = .30$, $SE = .15$, $p > .05$) suggesting that extended eye glances fully mediate the relationship between ADHD and driving problems. *Covarying ODD did not change this result.*

5.a.4 Efficacy of FOCAL intervention among non-ADHD teens^{18, 19}

Using a post-test only experimental design, 37 typical teen drivers (aged 16 and 17) were randomly assigned to FOCAL ($n = 19$) or a sham ($n = 18$) intervention consisting of *Rules of the Road* training. FOCAL consisted of the computerized intervention described in Section 5.d.1. Driver eye glance behavior during a road test was recorded using a portable lightweight eye-tracker installed in a car. Only 19.5% of glances of teens trained using FOCAL exceeded 2 secs compared to 28.8% of glances among those in the sham group [i.e., a 30% reduction; $F(1,35) = 4.57$, $p < .05$]. Teens were also tested in a driving simulator where a 50% reduction in the percentage of glances over a 2-sec threshold was observed among those who received FOCAL training compared to the sham intervention ($t_{38} = 3.30$, $p < .005$).

In a separate study¹⁸, 40 typical teens (aged 16-18) were randomly assigned to FOCAL or sham intervention. We demonstrated that the effect of training not only persists out to a 4-month follow-up assessment of visual attention during driving (FOCAL % of extended glances = 19% vs. sham = 29%, $t_{38} = 2.48$, $p < .05$) but are even stronger than immediate post-intervention assessment. In fact, the eye glance behavior of FOCAL-trained teens at 4-months post-intervention was not significantly different than rates of their parents (i.e., experienced drivers; percent of glances ≥ 2 secs for FOCAL trained teens = 19% vs. percent of glances ≥ 2 secs for experienced drivers = 11%).

5.a.5 Preliminary evidence of FOCAL+ efficacy in teens with ADHD

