5.f.2.a.1 Power Analyses for Testing Hypotheses 1 & 2: *Effect size estimates from our preliminary data (Section 5.a.5) suggest a single FOCAL+ training session improves extended eye glances among teens with ADHD with an effect size (Cohen's d) of 1.19. Since this effect size will surely diminish over the course of the 1-year of assessments, we used a conservative effect size estimate of .6 to power our research hypotheses. Monte Carlo simulation power analyses were performed under the following assumptions: (a) FOCAL+ effect size of .6, (b) effect size of .10 for our sham intervention, and (c) inclusion of months of driving experience as a covariate. Power analysis with these assumptions indicate that sample sizes of N = 41 per group will result in power $\geq .80$ to detect a significant main effect of Group indicating that the FOCAL+ intervention results in significantly fewer extended glances compared to the sham group at all post-baseline time points. We've powered our study with a larger sample size in order to detect potential moderators of treatment response (see Section 5.f.2.c below). Using the proposed sample size of 68 participants per group will provide use with 99% power to detect treatment effects.*

While data has been collected examining the efficacy of the FOCAL+ intervention on extended eye glances, the efficacy of the FOCAL+ intervention on driver performance has not been addressed. However, we assume a comparable intervention effect for FOCAL+ on driving outcomes based on the following pieces of evidence. Since the Pearson correlation between extended eye glances and collision events in the driving simulator is .74⁴², we will assume that the effect size for intervention effects on driving outcomes will be

comparable to what has been found for extended glances and that we will have >90% power to detect intervention effects on driving performance outcomes as well.

Aim #3: *Examine how many FOCAL+ training sessions are required to normalize extended glances away from the roadway among teens with ADHD.*

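### The >90% power for driving performance rests on an unsupported assumption; if training acts on SDLP only through glances, the protocol's main-effect test has about 54–69% power

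*Combined protocol and SAP*

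**What the plan says.** Section 5.f.2.a.1 of the protocol gives these assumptions for glances: "a) FOCAL+ effect size of .6, (b) effect size of .10 for our sham intervention". Its simulations "indicate that sample sizes of N = 41 per group will result in power" of at least .80 for the main effect of group, and it adds: "Using the proposed sample size of 68 participants per group will provide use with 99% power to detect treatment effects".

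For driving outcomes no simulation is reported. The section concedes that "the efficacy of the FOCAL+ intervention on driver performance has not been addressed". It then cites a Pearson correlation of .74 between long glances and collision events in a simulator, and infers an effect "comparable to what has been found for extended glances and that we will have >90% power to detect intervention effects on driving performance outcomes".

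The outcome being powered is set in section 5.f.2.a: "To test Hypotheses 2, the primary dependent variable will be SDLP during driving simulation". Section 3.c reports the glance association for that outcome: "Extended glances away from the roadway accounts for 32.5% of the variance in standard deviation in lateral position (SDLP". Section 5.a.3 describes the mediation result as "suggesting that extended eye glances fully mediate the relationship between ADHD and driving problems", which is the rationale for training glances in order to improve driving.

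The SAP makes SDLP one of two primary endpoints (5.2). It tests Group x Timepoint contrasts against baseline (Primary Efficacy Analysis) at a Bonferroni alpha of .0125 (8.5.5). SAP section 7 raises the randomised number to 152, so that 136 have simulator outcomes, and states no power.

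**The concern.** If training improves driving by shortening glances, a gain of d standard deviations in glances implies a gain of r x d in the driving outcome, where r is the glance–outcome correlation. The protocol in effect sets r = 1. Its supporting correlation is also for another outcome, while its own glance–SDLP figure goes unused.

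This is the only power statement for the intervention effect on SDLP. A non-significant SDLP result could be set against the >90% and taken as good evidence that training does not change lane keeping, when the design may have had much less chance of detecting a change.

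**Working it through.** **Inputs.** 68 per arm and 41 per arm; power of at least .80 and 99%; effect sizes .6 and .10; r = .74 (all 5.f.2.a.1). R² = .325, so r = √.325 = .570 (3.c). SDLP test–retest .80 (5.e.1, driving simulation). Alpha .0125 (SAP 8.5.5). The protocol's power section states no alpha, so two-sided .05 is assumed. Power is from the two-sample t test with noncentrality d√(n/2) and 2n − 2 degrees of freedom.

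**Step 1: the plan's own figure.** The protocol does not give the within-subject correlation used in its simulations, so I solved for the effective d that its statements imply.
- 80% at 41 per arm: d = .626.
- 99% at 68 per arm: d = .740.

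Carried over to driving in full, these give 95% and 99% at 68 per arm. A plain d = .6 at one time point gives 93.5%. So >90% does follow if nothing is lost between glances and driving.

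**Step 2: how much may be lost.** At 68 per arm, 90% power needs d = .560. That is .560/.626 = 89% or .560/.740 = 76% of the glance effect.

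**Step 3: attenuation, protocol main-effect test, two-sided .05.**

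| r | d = r x .626 | power | d = r x .740 | power |
|---|---|---|---|---|
| .74 (collisions) | .463 | 77% | .548 | 89% |
| .57 (SDLP) | .357 | 54% | .422 | 69% |

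The low ends treat at least .80 at 41 per arm as exactly .80. The upper ends fit both statements, since d = .740 gives 91% at 41 per arm.

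**Step 4: the SAP's test.** This is a change-from-baseline contrast at one visit, alpha .0125, 68 per arm with data. With retest .80, the SD of change is √(2 x (1 − .80)) = .632 of the SDLP SD. The between-arm glance effect is taken as .6 − .10 = .5, up to .6.
- r = .57: .285/.632 = .451 gives 54%; .342/.632 = .541 gives 73%.
- r = .74: .370/.632 = .585 gives 81%; .444/.632 = .702 gives 94%.

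The retest value matters a great deal. At a retest of .5 the SD of change equals the SDLP SD (√(2 x .5) = 1), and the r = .57 figures fall to 20–30%. The protocol takes the .80 from a paper on the on-road driving test.

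**The case against.** The best defence is that the protocol says openly that it assumes a comparable effect, and under that assumption >90% is correct. That stands: the sum is not wrong, its premise is unsupported. On the 99% calibration the protocol's own .74 gives 89%, barely short of the claim. That stands as arithmetic, but .74 describes collisions.

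The r x d rule has its own weaknesses. It assumes no direct effect of training on SDLP. It takes a correlation from preliminary data as holding within the trial's arms. It also treats the glance count as error-free: with an assumed reliability of .7, .422/.7 = .603 gives 94%. The documents report no reliability for the count, so this cannot be settled.

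The calibrated d also gives SDLP the repeated-measures gain implied for glances. With retest .80, r = .57 and d = .5–.6, averaging four or five post-training assessments gives about 43–58% at .05. Adjusting a four-assessment average for baseline would give about 95–99%, but section 5.f.2.a lists only driving experience as a covariate.

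One could read the effect already found as the pilot d of 1.19, since 1.19 x .57 = .678 gives 97.5%. But that is a pre–post change within one arm of a 12-teen pilot, and the section itself scales it down to .6.

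A reader might go further in three ways.
- SDLP power simply is 54–69%. It is not: the range depends on the premises above.
- The coefficients in 5.a.3 (.10 indirect, .30 direct) show that glances carry only a quarter of the effect. They describe ADHD status and SDLP, not training and SDLP, and a partial share contradicts the through-glances premise behind r x d.
- No version of the design reaches 90%. Step 4 gives 94% with r = .74 and d = .6.

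**Conclusion.** The concern holds in conditional form. The >90% is an assumption supported by a correlation for a different outcome, and the protocol's own glance–SDLP association points lower. If the effect on SDLP runs wholly through glances, the protocol's main-effect test has about 54–69% power with r = .57 and 77–89% with r = .74. This assumes 68 per arm, two-sided .05 and the calibration in step 1. A direct effect on SDLP, or use of baseline SDLP, would raise these figures.

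They should not be read as the power of the SAP analysis, which uses another contrast and another alpha. On the same mediation premise, with d = .5–.6 and retest .80, that analysis has about 54–73% power with r = .57 and 81–94% with r = .74.

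The consequence is for how a null SDLP result is interpreted. The validity of the tests is not affected, and the confidence intervals the SAP requires already give some protection.

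**What to change.** In protocol section 5.f.2.a.1, withdraw the >90% statement. State instead an SDLP effect equal to the glance effect times .57 (range to .74), with the conditional power of 54–69% (77–89% with .74). Name the assumptions: the effect acts only through glances, two-sided .05, at least .80 read as exactly .80 for the low ends, and the glance-calibrated gain from repeated measures.

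Do not copy 54–69% into SAP section 7. There, give SDLP power for the SAP's own Group x Timepoint contrast at .0125: about 54–73% with r = .57 and 81–94% with r = .74, stating the assumed d of .5–.6 and retest of .80. Add that a non-significant SDLP result is to be read from its confidence interval and is not in itself evidence of no effect.

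The cost is a few sentences and a less favourable stated figure. Sample size, conduct and analysis are unchanged.
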